6.0 DRUG INFORMATION

6.1 Entinostat - Investigational Agent

6.1.1 Description

Entinostat is a synthetic orally available class I selective HDACi that belongs to the class of substituted pyridylcarbamates with a molecular weight of 376.4. Entinostat belongs to the pharmacologic class of antineoplastic agents.

6.1.2 Supplier/How Supplied/Storage/Handling

Investigational supply of entinostat will be provided at no cost to the patient by Syndax Pharmaceuticals.

Entinostat is an oral drug supplied by SYNDAX as pink to light red (1 mg) or yellow (5 mg) polymorph B coated tablets. Each tablet contains mannitol, sodium starch glycolate, hydroxypropyl cellulose, potassium bicarbonate, and magnesium stearate as inert fillers. The film coating consists of hypromellose, talc, titanium dioxide, and ferric oxide pigments (red and yellow) as colorants. Entinostat is to be stored at controlled room temperature (15°C to 25°C) in a secure, locked storage area to which access is limited. Entinostat is to be protected from light and not to be exposed to extremes of temperature (greater than 30°C or less than 5°C). The pharmacist should dispense the investigational material to the patient at appropriate intervals throughout the study in childproof containers.

6.1.3 Dosage and Administration

Entinostat is to be taken on an empty stomach, at least 2 hours after a meal and at least 1 hour before the next meal. If entinostat is vomited, dosing should not be re-administered but instead the dose should be skipped.

For weekly (or less frequent) dosing: If an entinostat dose is missed, it may be taken up to 48 hours after the scheduled dosing time. If it is not taken within the 48-hour window, the dose should not be taken and should be counted as a missed dose. The patient should take the next scheduled dose per protocol.

6.1.4 Entinostat Compliance

Treatment compliance for entinostat dosing will be assessed at the end of each cycle, defined as 3 weeks (21 days). The first cycle on study will consist only of entinostat (mono-therapy). All 21-day cycles of treatment on study thereafter will include entinostat in combination with pembrolizumab. Patients will complete the IRB-approved dosing diary for documenting date and time of each weekly entinostat dose. Subjects will be instructed to bring all study IP (including partially used bottles) to each visit, including their subject dosing diary. The dates of any missed doses will also be recorded in the subject dosing diary. Site staff will perform accountability of the returned drug. Patient compliance will be assessed.

Site staff must ensure that the patient clearly understands the directions for self-administration of study drug and complies with the schedule provided.

6.1.5 Drug Accountability

The investigator, or designee, is responsible for keeping accurate records of the clinical supplies received from the company sponsor or designee. The total amount of drug dispensed to subjects and amount remaining at trial conclusion will be documented. The amount dispensed, amount returned, date dispensed, date returned, and lot number is to be recorded for each patient as applicable. The amount of drug dosed and start date for each dose will be recorded. An accurate and current accounting of the dispensing and return of entinostat for each subject will be maintained on an ongoing basis by a member of the study site staff. The amount of study drug dispensed and returned for individual subjects will be recorded in the Investigational Drug Accountability Record.

6.1.6 Return and Retention of Study Drug

Upon completion or termination of the study, all unused and/or partially used investigational product will be destroyed at the site per institutional policy (e.g., UNC IDS drug destruction policy). It is the Investigator's responsibility to arrange for disposal of all empty containers, provided that procedures for proper disposal have been established according to applicable federal, state, local and institutional guidelines and procedures, and provided that appropriate records of disposal are kept.

6.1.7 AEs Associated with Investigational Drug

As of July 1, 2016, entinostat has been given to >1,055 cancer patients in 31 clinical research studies in the mono-therapy setting and combination setting with another agent(s).

The following side effects occurred in more than 20% of patients with cancer, receiving entinostat alone. These events may or may not be related to entinostat.

- Fatigue (tiredness),
- Nausea,
- Thrombocytopenia,
- Anemia,
- Vomiting,
- Neutropenia,
- Diarrhea,
- Leukopenia,
- Feeling not hungry (decreased appetite),
- Hypophosphatemia,
- Hyponatremia,
- Hypoalbuminemia,
- Headache.

The following side effects were seen in $\geq 10\%$ to 20% of patients, with cancer, treated with entinostat alone. These events may or may not be related to entinostat.

- Shortness of breath or difficulty breathing,
- Constipation,
- Hyperglycemia,
- Hypocalcemia,
- Hypokalemia,
- Swelling in the legs, feet and/or ankles,
- Increase in serum alkaline phosphatase,
- Leukopenia,
- Abdominal pain,
- Fever,
- Cough,
- Muscle pain,
- Salty, metallic taste,
- Indigestion,
- Dehydration.

The following SAE occurred in $\geq 5\%$ of patients with cancer, receiving entinostat alone. These events may or may not be related to entinostat.

- Fatigue,
- Shortness of breath or difficulty breathing,
- Decreased appetite,
- Neutropenia,
- Dehydration,
- Anemia,
- Fever,
- Nausea,
- Abdominal pain,
- Diarrhea,
- Infection,
- Thrombocytopenia.

Overall, the side effects of entinostat when given in combination with other anti-cancer agents were similar to that seen when entinostat was given alone.

6.2 Pembrolizumab (Keytruda™) - Commercial Drug

6.2.1 Description

Pembrolizumab is a humanized monoclonal antibody that blocks the interaction between PD-1 and its ligands, PD-L1 and PD-L2. Pembrolizumab is an IgG4κ immunoglobulin with an approximate molecular weight of 140 kD. Full prescribing information for pembrolizumab is available at:

http://www.merck.com/product/usa/pi_circulars/k/keytruda/keytruda_pi.pdf

6.2.2 **Dosage and Administration:**

Pembrolizumab (200 mg) will be administered IV over 30 min (range of infusion time, 25-40 min) every 21 days (i.e., three weeks) in combination with entinostat. Pembrolizumab should be given on D1 of each cycle, except for cycle 1, after entinostat dosing occurs assuming patient is not on a hold for entinostat.

6.2.3 **Storage and Stability:**

Solution for infusion vials should be stored at refrigerated conditions (2–8 °C) and protected from light.

Clinical supplies must be stored in a secure, limited-access location under the storage conditions specified on the label. Receipt and dispensing of trial medication must be recorded by an authorized person at the trial site.

Handling and Disposal: Local requirements for disposal of hazardous drugs should be followed at each participating clinical site.

Please see UNC policy on hazardous drugs:

<http://intranet.unchealthcare.org/intranet/hospitaldepartments/safetynet/policies/hazardousdrugs.pdf>

6.2.4 **Adverse Events Associated with Commercial Drug**

The most common AEs (reported in $\geq 20\%$ of patients in clinical trials of pembrolizumab) included fatigue, pruritus, diarrhea, decreased appetite, rash, pyrexia, cough, dyspnea, musculoskeletal pain, constipation, and nausea. The following warnings are associated with the use of pembrolizumab:

Immune-Mediated Pneumonitis

Pneumonitis occurred in $\sim 3\%$ of melanoma patients treated in clinical trials of pembrolizumab. The median time-to-development of pneumonitis was 5 months with a median duration of 4.9 months. The one patient with Grade 3 pneumonitis required initial treatment with high-dose systemic corticosteroids (greater than or equal to 40 mg prednisone or equivalent per day) followed by a corticosteroid taper. Pneumonitis completely resolved in seven of the nine patients with Grade 2-3 pneumonitis.

Immune-Mediated Colitis

Colitis occurred in 1% of melanoma patients treated in clinical trials of pembrolizumab. The median time-to-onset was 6.5 months with a median duration of 2.6 months. All three patients with Grade 2 or 3 colitis were treated with high-dose corticosteroids (greater than or equal to 40 mg prednisone or equivalent per day).

Immune-Mediated Hepatitis

Autoimmune hepatitis occurred in 0.5% of melanoma patients treated in clinical trials of pembrolizumab. The time-to-onset was 22 days for the case of Grade 4 hepatitis, which lasted 1.1 months. The patient with Grade 4 hepatitis permanently discontinued pembrolizumab and was treated with high-dose (≥ 40 mg prednisone or equivalent per day) systemic corticosteroids followed by a corticosteroid taper. Both patients with hepatitis experienced complete resolution of the event.

Immune-Mediated Hypophysitis

Hypophysitis occurred in 0.5% of melanoma patients treated in clinical trials of pembrolizumab. The time-to-onset was 1.7 months for the patient with Grade 4 hypophysitis and 1.3 months for the patient with Grade 2 hypophysitis. Both patients were treated with high-dose (greater than or equal to 40 mg prednisone or equivalent per day) corticosteroids followed by a corticosteroid taper and remained on a physiologic replacement dose.

Renal Failure and Immune-Mediated Nephritis

Nephritis occurred in 3 (0.7%) patients of melanoma patients treated in clinical trials of pembrolizumab, consisting of one case of Grade 2 autoimmune nephritis (0.2%) and two cases of interstitial nephritis with renal failure (0.5%), one Grade 3 and one Grade 4. The time-to-onset of autoimmune nephritis was 11.6 months after the first dose of pembrolizumab (5 months after the last dose) and lasted 3.2 months; this patient did not have a biopsy. Acute interstitial nephritis was confirmed by renal biopsy in two patients with Grades 3-4 renal failure. All three patients fully recovered their renal function with treatment with high-dose corticosteroids (≥ 40 mg prednisone or equivalent per day) followed by a corticosteroid taper.

Immune-Mediated Hyperthyroidism

Hyperthyroidism occurred in 5 (1.2%) of 411 melanoma patients treated in clinical trials of pembrolizumab. The median time-to-onset was 1.5 months and the median duration was 2.8 months (range 0.9 to 6.1 months). One of two patients with Grade 2 and the one patient with Grade 3 hyperthyroidism required initial treatment with high-dose corticosteroids (greater than or equal to 40 mg prednisone or equivalent per day) followed by a corticosteroid taper. One patient required permanent discontinuation of pembrolizumab due to hyperthyroidism. All five patients with hyperthyroidism experienced complete resolution of the event.

Immune-Mediated Hypothyroidism

Hypothyroidism occurred in 34 (8.3%) of 411 melanoma patients treated in clinical trials of pembrolizumab. The median time-to-onset of hypothyroidism was 3.5 months. All but two of the patients with hypothyroidism were treated with long-term thyroid hormone replacement therapy. The other two patients only required short-term thyroid hormone replacement therapy. No patient received corticosteroids or discontinued pembrolizumab for management of hypothyroidism. Thyroid disorders can occur at any time during treatment.

Other Immune-Mediated Adverse Reactions

Other clinically important immune-mediated adverse reactions can occur. The following clinically significant, immune-mediated adverse reactions occurred in less than 1% of patients treated with pembrolizumab, including exfoliative dermatitis, uveitis, arthritis, myositis, pancreatitis, hemolytic anemia, partial seizures arising in a patient with inflammatory foci in brain parenchyma, and adrenal insufficiency.

Across clinical studies with pembrolizumab in approximately 2,000 patients, the following additional clinically significant, immune-mediated adverse reactions were reported in less than 1% of patients: myasthenic syndrome, optic neuritis, and rhabdomyolysis.

Embryofetal Toxicity

Pembrolizumab may cause fetal harm when administered to a pregnant woman. Animal models link the PD-1/PD-L1 signaling pathway with maintenance of pregnancy through induction of maternal immune tolerance to fetal tissue.

Steven's Johnson Syndrome (SJS) and Toxic Epidermal Necrolysis (TEN)

The risk of SJS and TEN is reported at approximately 0.4–7 cases per million patient years in the general adult population. Independent risk factors include certain medications, such as anticonvulsants, sulfonamides, aminopenicillins, allopurinol, and NSAIDs. Non-medication triggers include infection, contrast media, and vaccinations. Malignancy is associated with an increased mortality rate in patients with SJS and TEN.

Myocarditis

A total of 6 cases of myocarditis have been reported in patients treated with pembrolizumab in clinical trials in an expanded access program. There was one fatal case reported in a clinical trial. Immune-mediated myocarditis should be suspected if other causes of myocarditis, such as infection or prior radiation therapy, have been excluded. Risk factors include certain medications and treatment modalities, such as radiation, anthracycline, alkylating agents and, most recently, checkpoint inhibitors.

6.3 Clinical Assessments

Clinical assessments will be performed as outlined in the Time and Events Table in Section 7.1.

6.3.1 Concomitant Medications

All concomitant medication and concurrent therapies will be documented at Baseline/Screening and throughout the study, as summarized in the Time and Events Table in Section 7.1. Dose, route, unit frequency of administration, and indication for administration and dates of medication will be captured.

6.3.2 Demographics

Demographic information (date of birth, gender, race) will be recorded at Screening.

6.3.3 Medical History

Relevant medical history, including history of current disease, patient demographics, other pertinent history and information regarding underlying diseases will be recorded at screening and a focused medical history on symptoms/toxicity will be performed thereafter.

6.3.4 Physical Examination

For screening: A complete physical examination, including height (at screening only), weight, examination of skin, ECOG performance status and vital signs (i.e., weight, temperature, blood pressure, heart rate, respiratory rate, oxygen saturation) will be performed at screening and the first study visit #. Qualified staff (MD, NP, RN, and PA) may complete the abbreviated physical exam (i.e., focused on symptoms/toxicity as noted below) at all other visits.

After screening starting on D1/Cycle 1/Wk1: physical exam should be focused on symptoms/toxicity including weight, examination of skin, ECOG performance status and vital signs thereafter. New abnormal physical exam findings must be documented and will be followed by a physician or other qualified staff at the next scheduled visit.

6.3.5 Adverse Events

Events should be assessed per NCI-CTCAE criteria v5.0. Information regarding occurrence of AEs will be captured throughout the study. Duration (start and stop dates), severity/grade, outcome, treatment and relation to study drug will be recorded in the CRF.

6.3.6 Disease Assessment

This following test should be performed for assessment of melanoma disease.

6.3.6.1 Computed tomography (CT) of the whole body i.e., neck (if applicable), chest, abdomen, pelvis with IV contrast (or abdominal/pelvis MRI if allergy to IV contrast)

Baseline (screening) disease assessment should be obtained within 21 days of initiating study treatment. During the study, scans will be repeated as outlined in the Time and Events table in section 7.1 (i.e., at the end of week 10[D1 of cycle 4 or Study day 64/Wk10], end of week 15 [D1 of cycle 6 i.e., Study day 106/Wk16], end of week 21 [D1 of cycle 8 or Study day 148/Wk22], and end of week 27). Scans obtained during study treatment may be performed within ± 7 days of the scheduled study visit.

6.3.6.2 *Magnetic Resonance Imaging (MRI) of the brain*

MRI of the brain must be obtained at baseline (screening) and at end of treatment (i.e., at time of disease progression or at week 27); on any other visit **only if clinically indicated**, as per standard of care. If brain MRI is not feasible, patient can have a CT scan with IV contrast.

6.3.7 **Pre-Screening Pathology Assessment Period (pre-screening only)**

Given the limited 21-day screening period, and the requirement for absent TIL/TAL in melanoma tissues, archival metastatic tissue (locoregional, distant metastatic) can be requested and assessed before study enrollment (pre-screening). There is not an official pre-screening period given that [name], study's pathologist, is UNC's sole melanoma pathologist and routinely signs off his pathology reports, either from outside consultation slides or from in-house cases, along with a report about the presence of absence of tumor-infiltrating/-associated lymphocytes. If not available already, representative tumor sections from archived tumor blocks will be stained with H&E and will be assessed by [name], study pathologist, for assessment of quality using these criteria: (1) the tumor surface area must be at least 1cm² (which can be from a combination of metastatic blocks if necessary), (2) no more than 20% of necrosis, (3) the ratio of viable tumor cells to tumor-associated stroma should be at least 60/40, and (4) if TILs are present based on H&E stained sections, they must be $\leq 1\%$ of the total number of cells in the specimen; the amount of tissue should be ≥ 1 cm².

If archival tissue is unavailable or insufficient, a fresh biopsy should be performed to confirm unresectable stage III or distant metastatic disease. If the patient qualifies, then they can sign the informed consent.

6.3.8 **Electrocardiogram (ECG)**

A 12-lead ECG will be performed at screening and on cycles 2, 4, 6, 8, as outlined in the Time and Events table.

6.3.9 **Patient Pill Diary (Entinostat)**

A patient pill diary will be checked at the beginning of each cycle and should be kept by subject for self-documentation of entinostat dosing (as outlined in the Time and Events table). A single 5 mg tablet is to be taken on day 1, day 8, and day 15 of each cycle within the specified 21-day cycle windows. See Section 6.0 for information on entinostat drug supply, storage, handling and compliance.

6.4 **Clinical Laboratory Assessments**

6.4.1 **Hematology**

Blood will be obtained and sent to the clinical site hematology lab for assessment of a complete blood count with differential (i.e., hemoglobin, hematocrit, red blood cell count, white blood cell count, white blood cell differential, and platelet count), as outlined in the time and events table.

Hematology labs should be performed pre-study and on D1 at every treatment cycle and at the end of treatment (i.e., D1C1, D1C2, D1C3, etc.), as outlined in the Time and Events Table.

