1.0 BACKGROUND AND RATIONALE

1.1 Study Synopsis

This is an exploratory (n=10-12 evaluable patients), open-label, single-arm, phase II study in patients with ‘non-inflamed’ unresectable regional or distant metastatic melanomas irrespective of prior treatment with PD-1/PD-L1 pathway inhibitors. The primary endpoint is to assess the incidence of histopathologic conversion of non-inflamed melanomas from patients with metastatic melanoma to ‘inflamed’ melanoma following single-agent entinostat “priming” (entinostat monotherapy). More specifically, patients with metastatic melanomas that have no evidence of tumor-infiltrating or tumor-associated lymphocytes (TIL/TAL), based on standard hematoxylin and eosin (H&E) staining of representative tumor sections (non-inflamed melanomas) will receive weekly entinostat for 3 weeks in cycle 1 (entinostat monotherapy; 5mg PO, qwk on D1, D8, D15 of cycle 1; cycle length = 21 days). Mandatory tumor tissue biopsies will be performed in the end of cycle 1, beginning of cycle 2 (day 22±2 days), immediately before treatment with concurrent entinostat (once weekly × 3) and pembrolizumab (200 mg q3wks) in cycles 2-9 (see section 5.2.1 drug dosing schema). Correlative studies will be performed at baseline and in the end of cycle 1, beginning of cycle 2 (day 22±2 days) to assess whether: (a) 3 weeks of entinostat monotherapy converts TIL/TAL-absent melanomas to TIL/TAL-present by histopathologic (H&E stain) analysis, (b) 3 weeks of single-agent entinostat induces changes in gene expression profiling by assessing distinct signatures as defined by RNA-sequencing signatures (RNA-seq; ‘immune-high’, innate anti-PD-1 resistance [IPRES], and epigenetic¹⁻³), (c) 3 weeks of single-agent entinostat induces changes in histone-accessible DNA by performing formaldehyde-assisted isolation of regulatory elements (FAIRE)⁴, (d) conversion of non-inflamed to inflamed melanomas by single-agent entinostat and/or antitumor response to the entinostat-pembrolizumab combination is associated with a baseline signature that consists of distinct somatic mutation gene profile, global histone modification profile in melanoma tissue or peripheral blood mononuclear cells (PBMC), and/or abundance of entinostat targets in melanoma cells (HDAC 1, 2, 3, and 11). Up to 12 evaluable patients will be treated with entinostat plus pembrolizumab for up to 27 weeks (approximately 6 months) based on clinical benefit. Patients who continue to have clinical benefit at 27 weeks may continue therapy with pembrolizumab or any other PD-1/PD-L1 inhibitor, as per standard of care.

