1.7 Correlative Studies

The study contains a single integral tumor tissue biomarker and several exploratory tumor tissue and peripheral correlative biomarkers.

1.7.1 Integral Biomarker. Assessment of TIL/TAL in representative H&E-stained sections from archived tumor tissues to determine eligibility for the trial during screening.

Since the primary endpoint of the study is to assess the incidence of conversion of non-inflamed vs. inflamed melanoma following 3 weeks of entinostat monotherapy, we will use a cost-efficient assay to determine eligibility, namely assessment of TIL/TALs in archived metastatic melanoma specimens. Since the presence of TIL/TALs can be heterogeneous within the same tissue as well as across different metastatic sites, the following are requirements for archived tumor tissue eligibility:

- The amount of surface area corresponding to melanoma devoid of stroma should be at least 1cm². This ensures sufficient tumor to be screened for presence of TIL/TALs, yet it is NOT too restrictive for patients who do not have “sufficiently large” archived tumor specimen for analysis.

- No more than 20% of necrosis is allowed; this ensures that high quality specimens are available for analysis.
- At least 60% of viable melanoma cells are present; this ensures that the melanoma cell compartment is sufficiently larger than the stromal component.
- Must have available archival tissue and subjects must have consented to allow collection of archived tumor blocks from previous surgeries confirming or treating unresectable stage III or distant metastatic disease. If more than one archived tumor block is available, only one block is required to be analyzed for the presence of TIL/TALS. Archived tumor tissues must fulfill the following criteria based on representative H&E-stained tissue sections: (1) the tumor surface area must be $\geq 1\text{cm}^2$ (which can be the sum tumor surface from more than metastatic blocks, if necessary), (2) $\leq 20\%$ of necrosis, (3) the ratio of viable tumor cells to tumor-associated stroma should be $\geq 60/40$, and (4) if TILs are present based on H&E stained sections, they must be $\leq 1\%$ of the total number of cells in the specimen.
- If more than one archived metastatic melanoma specimen is available during the 21-day screening period, only one block is required to be analyzed for the presence of TIL/TALs.

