4.1 Inclusion Criteria

- 4.1.1 Age \geq 18 years at the time of consent.
- 4.1.2 Subject has provided informed consent and HIPAA prior to initiation of any study-specific activities/procedures.
- 4.1.3 ECOG Performance Status of ≤ 2 .
- 4.1.4 Histologically confirmed metastatic (regional or distant) melanoma of any subtype (cutaneous, mucosal, ocular).
- 4.1.5 AJCC stage unresectable III or stage IV disease that is measurable by RECIST v1.1 criteria.
- 4.1.6 Must agree to undergo one on-treatment tumor biopsy on day 22 (± 2 days) of the study. Subjects for whom fresh samples cannot be safely provided (e.g., inaccessible tumor for biopsy) will not be eligible for study participation.
- 4.1.7 Must have available archival tissue and subjects must have consented to allow collection of archived tumor blocks from previous surgeries confirming or treating unresectable stage III or distant metastatic disease. If more than one archived tumor block is available, only one block is required to be analyzed for the presence of TIL/TALS. Archived tumor tissues must fulfill the following criteria based on two representative H&E-stained tissue sections: (1) the tumor surface area must be at least 1cm^2 (which can be from a combination of metastatic blocks if necessary), (2) no more than 20% of necrosis, (3) the ratio of viable tumor cells to tumor-associated stroma should be at least 60/40, and (4) if TILs are present based on H&E stained

sections, they must be $\leq 1\%$ of the total number of cells in the specimen; the amount of tissue should be ≥ 1 cm².

[name], study pathologist, must sign off on the eligibility of archived tumor blocks before study enrollment. If archival tissue is unavailable or insufficient, fresh biopsy should be performed to confirm unresectable stage III or distant metastatic disease.

4.1.8 Previous treatment with immune checkpoint inhibitors and chemotherapies is allowed on condition that the last treatment is at least 28 days prior to first dose of entinostat. Previous treatment with targeted therapies (e.g. MAPK inhibitors) is allowed on condition that the last treatment was administered at least 15 days prior to first dose of entinostat).

4.1.9 Demonstrate adequate organ function as defined in the table below; all screening labs to be obtained within 21 days prior to entinostat treatment.

System	Laboratory Value
Hematological*	

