9.2 Sample Size, Accrual and Duration of Accrual

Our goal is to enroll at least 10 evaluable patients. The immune-mediated mechanism of action of entinostat alone (primary translational endpoint) will be evaluated on representative H&E-stained tissue sections from tumor tissues collected at baseline and on day 22 by standard pathology analysis. This analysis will be conducted by [name], study pathologist. Density of TIL/TALs in these H&E-stained sections will be scored as a 0, 1+ (non-brisk), 2+ (brisk) ordinal variable¹⁵¹. By definition, upon enrollment if TILs are present based on H&E stained sections, they must be $\leq 1\%$ of the total number of cells in the specimen. A non-inflamed melanoma may have been ‘successfully’ converted to an inflamed melanoma following 21 days of entinostat ‘priming’ if the histopathologic analysis of day 22 melanoma biopsies shows any (i.e. brisk or non-brisk) evidence of TIL/TAL. In other words, we will capture the incidence of conversion as a dichotomous variable, present (i.e. brisk or non-brisk) or absent. Twenty-one days of entinostat ‘priming’ would be considered to have an immunomodulatory effect if at least 3 out of 10 evaluable patients show conversion of their melanomas from ‘non-inflamed’ to ‘inflamed’. This test has a type I error rate of 0.04 if the true rate is 0.08 and power of 83% if the true rate is 0.4.

The secondary endpoint is antitumor response by RECIST 1.1. Given that one of the determinants of response to single-agent PD-1 inhibitors is pre-existing TIL/TAL²⁹, we postulate that patients with metastatic melanoma and zero TIL/TAL will have nearly zero response rate. With 10 patients the exact 95% confidence interval for response rate is (0, 0.31) if 0 responses are observed out of 10 patients, and (0, 0.45) if 1 response is observed out of 10 patients.

Assuming that 20% of patients will not be evaluable due to screen failure, toxicity or rapid disease progression, and another 30% of enrolled patients will not have interpretable tumor biopsies on day 22 due to necrosis, stromal contamination or overall low quality, the total number of enrolled patients should be set to 14.

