APPENDIX C ARCHIVED TUMOR TISSUE FOR ENROLLMENT

Below is a sample letter (e-mail of this form is also acceptable) from the pathologist stating the adequacy of archived of tumor tissue for patient eligibility

Dear [name],

I have reviewed the hematoxylin and eosin-stained (H&E) slides corresponding to [SCREENING SUBJECT ID NUMBER and SUBJECT INITIALS]'s [PATIENT'S NUMBER OF AVAILABLE METASTATIC MELANOMA TISSUE BLOCKS) archived tumor block from the [PATIENT'S DIFFERENT PATHOLOGY ACCESSION NUMBERS CORRESPONDING TO PREVIOUS STANDARD OF CARE SURGICAL OR BIOPSY PROCEDURES]. I have confirmed that:

- The total tumor surface area from all the melanoma tissue blocks I have reviewed is at least 1 cm². will release 11-15 5-micron tissue section on charged slides to your institution for research analysis.
- The tumor contains no more than 20% necrosis
- The ratio of melanoma to stroma cells is at least 60:40.
- I attest that none of the H&E slides I have reviewed contains evidence of $\geq 1\%$ tumor-infiltrating or tumor-associated mononuclear cells.
- I attest that the total volume of corresponding tumor tissue that is contained within these block(s) is sufficient to yield fifteen (15) 10-micron tumor sections for your molecular correlative studies (i.e. FoundationOne® testing, RNA-seq, FAIRE analysis)
- I attest that the total volume of corresponding tumor tissue that is contained within these block(s) is sufficient to yield addition ten (10) 5-micron tumor sections for your tumor imaging correlative studies (immunohistochemistry and/or immunofluorescence)

Sincerely,

[name]
[PRINTED NAME AND MAILING ADDRESS]

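### Entry rules tolerate a low-level lymphocyte infiltrate, and disagree on which cells and what cut-off, while any TIL/TAL on day 22 counts as conversion, so an unchanged tumor could count as a success

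*Combined protocol and SAP*

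**What the plan says.** **Numbered criterion.** Section 4.1.7 sets four conditions on archived tissue. The last begins "and (4) if TILs are present based on H&E stained" and caps these cells at 1% or less of all cells in the specimen. Sections 1.7.1 and 6.3.7 carry the same item (in 6.3.7, "4) if TILs are present based on H&E stained sections, they must be" at most 1%), and 9.2 restates it as the definition at enrollment. None of these four statements of the cap names TAL.

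**Wording that covers TAL.** The synopsis (1.1) describes "metastatic melanomas that have no evidence of tumor-infiltrating or tumor-associated lymphocytes (TIL/TAL", with no tolerance. Section 1.7.1 names the integral biomarker as "Assessment of TIL/TAL in representative H&E-stained sections from archived tumor tissues to determine eligibility for the trial during screening". Section 2.1 defines non-inflamed as TIL/TAL-absent, and 5.1 asks for tissue that confirms absence. Section 6.3.7 opens with "the requirement for absent TIL/TAL in melanoma tissues" and then lists the TIL-only cap in the same paragraph.

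**Pathologist's letter.** In the Appendix C sample, the pathologist attests that no reviewed slide shows 1% or more "tumor-infiltrating or tumor-associated mononuclear cells".

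**Endpoint.** Section 3.1 describes a change between baseline and post-entinostat sections. Section 9.2 grades TIL/TAL density as 0, 1+ or 2+, then reduces it to present or absent. A tumor may count as converted "if the histopathologic analysis of day 22 melanoma biopsies shows any (i.e. brisk or non-brisk) evidence of TIL/TAL". At least 3 conversions in 10 evaluable patients is taken as an immunomodulatory effect, with a type I error of 0.04 at a true rate of 0.08 and power of 83% at 0.4.

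**The concern.** The entry rule and the success rule do not meet at the same line. Entry, by the numbered criterion, tolerates some lymphocytes. Success requires only that some are seen on day 22. Nothing in the 9.2 definition asks whether the patient had fewer before treatment. A tumor that enters with a small permitted infiltrate and is unchanged after three weeks of entinostat can therefore be recorded as converted.

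The entry passages also disagree on cell type (TIL, TIL/TAL or mononuclear cells), on the limit (absent, at most 1% or below 1%) and on the basis (the whole specimen or each slide). Which passage governs decides who enrolls.

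Conversion is the primary endpoint and three events decide it, so one or two tumors counted without change would matter. The analysis also leans on the strict reading: 9.2 bases its expectation of a near-zero response rate on patients with no TIL/TAL, and 9.3.1 expects none at baseline. Criterion (4) does not secure this.

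**Working it through.** **1. The rules side by side**

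| Place | Cells | Limit | Basis |
|---|---|---|---|
| 1.1, 2.1, 5.1, opening of 6.3.7 | TIL and TAL | absent | tumor tissue or sections |
| Criterion (4) in 1.7.1, 4.1.7, 6.3.7; restated in 9.2 | TIL | ≤1% | all cells in the specimen |
| Appendix C sample letter | infiltrating or associated mononuclear cells | <1% | every slide reviewed |
| 9.2, day 22 | TIL and TAL | any = converted | present (1+ or 2+) or absent (0) |

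**2. Three unchanged tumors.** Each is assumed to be read as present on day 22.

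- TIL above zero but below 1%, no TAL: passes criterion (4) and Appendix C, fails the absent wording, and counts as converted.
- TIL at exactly 1%, no TAL: passes criterion (4), cannot be attested under Appendix C, and counts as converted if enrolled.
- TIL at most 1% with substantial TAL: passes criterion (4) read literally, fails Appendix C and the absent wording, and counts as converted if enrolled.

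The first tumor shows that the problem is not confined to TAL. It passes both numerical entry rules.

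**3. The plan's own figures.** Inputs from 9.2: n = 10, success at 3 or more, null rate 0.08, alternative 0.40.

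- Type I error: 1 − 0.92^10 − 10(0.08)(0.92^9) − 45(0.08²)(0.92^8) = 1 − 0.4344 − 0.3777 − 0.1478 = 0.0401. The stated 0.04 is reproduced.
- Power: 1 − 0.6^10 − 10(0.4)(0.6^9) − 45(0.4²)(0.6^8) = 1 − 0.0060 − 0.0403 − 0.1209 = 0.8327. The stated 83% is reproduced.

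**4. Effect of k patients who count as converted without change.** Assume the other 10 − k convert independently at 0.08. The false-positive probability is P[Binomial(10 − k, 0.08) ≥ 3 − k].

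- k = 0: 0.0401
- k = 1: 1 − 0.92^9 − 9(0.08)(0.92^8) = 1 − 0.4722 − 0.3695 = 0.158
- k = 2: 1 − 0.92^8 = 1 − 0.5132 = 0.487
- k = 3: 1.00

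**5. The same effect by share.** The documents give no share f of such tumors, so this is an assumed range. The per-patient rate becomes 0.08 + 0.92f.

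- f = 5%: rate 0.126, P(≥3 of 10) = 0.122
- f = 10%: rate 0.172, P = 0.240
- f = 20%: rate 0.264, P = 0.516
- f = 30%: rate 0.356, P = 0.751

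**The case against.** A reader might infer that eligibility restricts only TIL, so that tumors with plain TAL enter freely. The documents do not support that. The synopsis, 2.1, 5.1 and the opening of 6.3.7 all require TAL to be absent too, and 1.7.1 makes TIL/TAL the eligibility biomarker. Section 4.1.7 requires the study pathologist to sign off before enrollment, and the Appendix C letter covers associated cells. In criterion (4), TIL may well be shorthand for both. A tumor with substantial TAL would probably be stopped.

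This narrows the point but does not remove it. Section 4.0 requires subjects to meet the listed criteria, and the listed cap names TILs. Appendix C is a sample letter, and the sign-off sentence in 4.1.7 does not refer to it. Even if the letter is always used, infiltrate below 1% passes.

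A second defense is that 3.1 speaks of change and 9.2 of converting a non-inflamed tumor, so an unchanged tumor could not count. That is a fair reading of intent. The operational rule in 9.2, however, is presence on day 22, with no comparison to the patient's own baseline.

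Third, the size is conditional, and this stands. No share is given. Section 1.7.1 says infiltrate can vary within a tissue and across metastases, so a small baseline infiltrate need not be seen again on day 22. Nor does 9.2 explain the null rate of 0.08; if it was meant to allow for some such readings, part of the excess is already counted.

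**Conclusion.** The inconsistency is real and goes beyond editing. As written, the entry criterion and the endpoint definition together let a tumor with a permitted low-level infiltrate (TIL, or TAL if criterion (4) is applied literally) count as converted without change. Separately, a tumor at exactly 1% TIL is eligible under 4.1.7 but cannot be attested under Appendix C.

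The number of patients affected is unknown. A reader might take 0.158 or 0.487 as the trial's actual type I error; the documents do not support that. These are illustrations for one and two such patients in 10, and they rest on two assumptions: a null rate of 0.08 for the remaining patients, and the baseline infiltrate being read as present on day 22. They show how little misclassification the 3-of-10 rule can absorb: one patient raises the error to about four times the stated 0.04 (0.158 / 0.040 ≈ 4). If no such patient enrolls, the stated error holds at a null rate of 0.08. The plan should be corrected, because its wording does not ensure that.

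**What to change.** 1. Reconcile 1.7.1, 4.1.7, 6.3.7, 9.2 and Appendix C to one baseline definition covering TIL and TAL together, with the same cell type, the same cut-off on the same side, and the same per-slide basis. Bring the absent wording in 1.1, 2.1 and 5.1 into line with it.
2. Score the baseline and day-22 sections on the same TIL/TAL scale, and record both readings for each patient. State how the percentage cut-off relates to the 0, 1+ and 2+ grades.
3. In 9.2, count conversion only when the day-22 reading exceeds both the baseline eligibility cut-off and the patient's own baseline score.

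Step 1 alone is not enough: with TIL and TAL both capped near 1%, an unchanged infiltrate below 1% would still count as any TIL/TAL on day 22. Step 3 closes that gap.

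The cost is wording in these sections and the letter, possibly a few more screen failures, and a slightly stricter conversion count. No new procedure is needed, since 6.3.7 says the study pathologist already reports infiltrating and associated lymphocytes routinely.
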